### 3.4 Secondary Endpoints

The first secondary endpoint will be to establish the timing of thrombus propagation for those individuals who have suffered such an event. The date of thrombus propagation confirmation will be compared to the date of the original DVT diagnosis for this purpose.

The second secondary outcome will include an assessment of net clinical benefit or harm as the composite of the primary efficacy outcome or the principal safety outcome up to day 90.

## 4 Subject Selection Enrollment and Withdrawal

### 4.1 Inclusion Criteria

1. Age range:  $\geq 18$  years
2. Both males and females
3. Confirmed acute calf vein thrombosis confined to either the deep (posterior tibial, anterior tibial, or peroneal) or muscular (gastrocnemius or soleal) veins.
4. Negative serum or urine pregnancy test done (within 2 weeks) prior to randomization, for women of childbearing potential only. Note: A Women of childbearing potential (WOCBP) is defined as any female who has experienced menarche and who has not undergone surgical sterilization (hysterectomy or bilateral oophorectomy) and is not postmenopausal. Menopause is defined as 12 months of amenorrhea in a woman over age 45 years in the absence of other biological or physiological causes.
5. Ability to provide written informed consent.

### 4.2 Exclusion Criteria

1. Any of the following because this study involves an investigational agent whose genotoxic, mutagenic and teratogenic effects on the developing fetus and newborn are unknown:
  - Pregnant women
  - Nursing women
  - Men or women of childbearing potential who are unwilling to employ adequate contraception

**Note:** Women of child bearing potential must agree to follow instructions for method(s) of contraception for the duration of treatment with study drug(s) plus 33 days after finishing the last dose.

Males who are sexually active with WOCBP must agree to follow instructions for method(s) of contraception for the duration of treatment with study drug(s) plus 93 days after finishing the last dose.

Azoospermic males and WOCBP who are continuously not heterosexually active are exempt from contraceptive requirements. However they must still undergo pregnancy testing as described in this section.

**Note:** Investigators shall counsel WOCBP and male subjects who are sexually active with WOCBP on the importance of pregnancy prevention and the implications of an unexpected pregnancy. Investigators shall advise WOCBP and male subjects who are sexually active with WOCBP on the use of highly effective

methods of contraception. Highly effective methods of contraception have a failure rate of < 1% when used consistently and correctly.

At a minimum, subjects must agree to the use of one method of highly effective contraception as listed below:

### **HIGHLY EFFECTIVE METHODS OF CONTRACEPTION**

- Male condoms with spermicide
- Hormonal methods of contraception including combined oral contraceptive pills, vaginal ring, injectables, implants and intrauterine devices (IUDs) such as Mirena® by WOCBP subject or male subject's WOCBP partner.
- Female partners of male subjects participating in the study may use hormone based contraceptives as one of the acceptable methods of contraception since they will not be receiving study drug,
- IUDs such as ParaGard®,
- Tubal ligation
- Vasectomy.
- Complete Abstinence\*

\*Complete abstinence is defined as complete avoidance of heterosexual intercourse and is an acceptable form of contraception for all study drugs.

Acceptable alternate methods of highly effective contraception must be discussed in the event that the subject chooses to forego complete abstinence

2. Acute co-existing proximal DVT (popliteal, femoral, iliac veins or IVC), pulmonary embolism, splanchnic vein thrombosis, cerebral venous sinus thrombosis within the past 3 months for whom anticoagulation therapy is indicated.
3. Age < 18 years.
4. Continuous treatment with therapeutic anticoagulant for more than 72 hours pre-randomization.
5. Contraindication to anticoagulant therapy
6. Significant kidney disease. Creatinine clearance < 25 ml/min using the Cockcroft-Gault equation:  $GFR = (140\text{-age}) * (\text{Wt in kg}) * (0.85 \text{ if female}) / (72 * \text{Cr})$ . (within last four weeks)
7. Significant liver disease (e.g. acute hepatitis, chronic active hepatitis, cirrhosis) or ALT (or AST) > 3 x ULN. (within last four weeks)
8. Platelet count <  $50 \times 10^9 / \text{L}$ . (within last four weeks)
9. Life expectancy < 12 months.
10. Current active bleeding.
11. Concomitant use of strong CYP3A4 inhibitors (e.g., HIV protease inhibitors, systemic ketoconazole) or strong CYP 3A4 inducers like rifampicin.
12. Active cancer defined as any evidence of cancer on cross-sectional imaging or cancer treatments within the past 6 months (chemotherapy, radiation therapy or cancer related surgery).
13. Anticipated need for urgent/emergent surgery or major invasive procedure.

14. Dual antiplatelet therapy (thienopyridine plus aspirin) and/or aspirin greater than 165 mg while on study medication.

### **4.3 Subject Recruitment, Enrollment and Screening**

This is a multi-Mayo center, randomized, double blind, placebo controlled, superiority trial for efficacy. Experienced data management personnel enroll patients, collect clinical trial data and ensure quality control. Patient registration occurs using centralized registration and randomization systems to ensure patient eligibility. The Research Radiology Core provides radiological image management including a centralized system of image collection, archiving and review for clinical studies. The Research Pharmacy Core offers a central pharmacy service, along with quality-control systems for medication order fulfillment, shipment and reconciliation.

Patients will be recruited from two potential sources, hospital in-patients and outpatients attending anticoagulation clinics at one of three sites: Mayo Clinic Rochester, Mayo Clinic Eau Claire, or Mayo Clinic La Crosse. Upon subject identification, the study will be explained in detail by the investigators or study coordinator, the consent form reviewed, questions answered, and the consent form signed.

#### **4.3.1 Recruitment of Patients**

We anticipate that a sizable percentage of patients will be recruited from Mayo Clinic Rochester. Patients will be recruited from Mayo Clinic Rochester, Mayo Clinic Eau Claire, or Mayo Clinic La Crosse.

### **4.4 Early Withdrawal of Subjects**

#### **4.4.1 Study Endpoint Achieved**

A small percentage of patients will meet either a thrombotic or bleeding outcome event as part of trial participation. These outcomes may be clinically symptomatic or may be identified as part of either the serial ultrasound imaging protocol or cross-sectional imaging obtained for other clinically indicated conditions.

##### **1. Thrombotic endpoint:**

- a.** If the patient suffers a symptomatic or asymptomatic thrombotic recurrence which is confirmed by cross-sectional imaging, then the study medication should be discontinued and the patient should be initiated on an alternate therapeutic anticoagulant based on guideline recommendations. Alternate anticoagulants could include enoxaparin/warfarin, rivaroxaban, edoxaban or dabigatran.
- b.** If the serial ultrasound imaging clearly identifies thrombus propagation which remains confined to the calf veins, then the study medication should be discontinued and the patient should be initiated on an alternate therapeutic anticoagulant based on guideline recommendations.
- c.** During normal business hours, the patient may be unblinded by contacting the Central Office (see page 1 of protocol). The Central Office will seek approval from the PI or a delegated Investigator prior to unblinding. During emergency circumstances where patient safety is felt to be compromised, study allocation can

be rapidly determined by drawing a heparin antiXa activity measure. If the patient is allocated to apixaban, the level will be elevated, unless they are not taking their medication. For patients allocated to placebo the levels will be undetectable. The unblinding site must notify the central office of the unblinding event within 72 hours of becoming aware.

## 2. Hemorrhagic endpoint:

- a. Non-major Clinically Relevant Bleed:** If the patient suffers a non-major clinically relevant bleed, then the study medication should be temporarily discontinued until the site and circumstances of the bleeding event have been evaluated. If these circumstances can be rectified, then the patient can remain on the study medication which will be restarted as soon as clinically indicated.
- b. Major Bleed:** If the patient suffers a major bleed, then the study medication should be discontinued and the patient cared for as clinically appropriate. Under these circumstances, the patient will be unblinded to determine the specific study medication (apixaban or matching placebo) by contacting the Central Office (see page 1 of protocol). During emergency circumstances where patient safety is felt to be compromised, study allocation can be rapidly determined by drawing a heparin antiXa activity measure. If the patient is allocated to apixaban, the level will be elevated, unless they are not taking their medication. For patients allocated to placebo the levels will be undetectable. The unblinding site must notify the central office of the unblinding event within 72 hours of becoming aware. Whether to restart an alternative anticoagulant will be left at the discretion of the medical care provider attending the patient.
- c. Life-threatening Bleed:** If the patient suffers a life-threatening bleed, then the study medication should be discontinued and the patient cared for as clinically appropriate. During emergency circumstances where patient safety is felt to be compromised, study allocation can be rapidly determined by drawing a heparin antiXa activity measure. If the patient is allocated to apixaban, the level will be elevated, unless they are not taking their medication. For patients allocated to placebo the levels will be undetectable. The unblinding site must notify the central office of the unblinding event within 72 hours of becoming aware. During normal business hours, the patient may be unblinded by contacting the Central Office (see page 1 of protocol). Treatment may include the use of prothrombin complex concentrates (K-Centra) depending on which study medication the subject was receiving (apixaban or placebo). Once the specific antidote for direct oral factor Xa inhibitors, andexanet alpha, has been FDA approved, the use of this medicine would also be appropriate.

#### **4.4.2 When and How to Withdraw Subjects**

Conditions under which a subject may be withdrawn from the study prior to that subject completing all of the study related procedures may include:

1. Subject safety issues:
  - a. Major bleeding including life threatening bleeding. For patients suffering a major bleed, the clinical scenario will be reviewed by the primary care provider caring for the patient to determine study drug termination. The site or overall investigators can also assist with this decision making.
  - b. Thromboembolic Event. For patients suffering a thromboembolic event, study drug should be discontinued and an alternative anticoagulant initiated by the health care provider caring for the patient.
2. Failure of subject to adhere to protocol requirements.
3. Thrombocytopenia. For platelet counts below  $50 \times 10^9/L$ , the patient will be excluded from continued participation.
4. Development of severe renal impairment (creatinine clearance  $< 25 \text{ ml/min}$ ). Renal function assessment will not be followed for the purposes of this study but only if clinically indicated.
5. Development of severe hepatic impairment (LFTs  $> 3x \text{ ULN}$ ). Liver function assessment will not be followed for the purposes of this study but only if clinically indicated.
6. Subject decision to withdraw from the study (withdrawal of consent)

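### Sections 4.4.1 and 4.4.2 give conflicting rules on study drug after a major or life-threatening bleed and must be reconciled

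*Combined protocol and SAP*

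**What the plan says.** Section 4.4.1, under the hemorrhagic endpoint, sets three tiers.

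- **Item 2a, clinically relevant non-major bleed:** if such a bleed occurs, "then the study medication should be temporarily discontinued until the site and circumstances of the bleeding event have been evaluated". Study drug may be resumed once the cause has been dealt with.
- **Item 2b, major bleed:** "If the patient suffers a major bleed, then the study medication should be discontinued and the patient cared for as clinically appropriate". It goes on: "Under these circumstances, the patient will be unblinded to determine the specific study medication". It leaves one matter open: "Whether to restart an alternative anticoagulant will be left at the discretion of the medical care provider attending the patient".
- **Item 2c, life-threatening bleed:** "If the patient suffers a life-threatening bleed, then the study medication should be discontinued". Unblinding is described here as something that can be done, not as something that will be done.

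Section 4.4.2 lists conditions that may lead to a subject leaving the study early. Item 1a is introduced as "Major bleeding including life threatening bleeding" and says that, for a patient with a major bleed, "the clinical scenario will be reviewed by the primary care provider caring for the patient to determine study drug termination". It adds: "The site or overall investigators can also assist with this decision making". Item 1b, on thromboembolic events, contains no such review. It directs that study drug be stopped and another anticoagulant started, as section 4.4.1 item 1 also does.

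**The concern.** For the same event, a site finds an instruction to stop study drug in one section and a provider's decision on whether to stop it in the next. Someone who works from 4.4.1 stops the drug. Someone who works from 4.4.2 may keep the patient on it after review and believe that the protocol has been followed. A monitor has no single text against which to call a deviation.

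Major bleeding is a component of the trial's second primary objective and can be serious for the individual patient, so handling should not depend on which page was read. Item 2b also requires unblinding after a major bleed. If study drug were then continued under 4.4.2, a participant in a double-blind trial would be taking it with the allocation known.

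**Working it through.** The plan states no figure on this point, so there is nothing to reproduce. The check is a comparison of the two sections.

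**Step 1. Do the sections cover the same event?** Yes. Items 2b and 2c of 4.4.1 deal with major and life-threatening bleeds. Item 1a of 4.4.2 names both in its opening phrase.

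**Step 2. Do they govern the same thing?** Yes. The lead-in to 4.4.2 is about leaving the study, but the sentence in item 1a is expressly about ending study drug, as are 2b and 2c.

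**Step 3. Do they give the same rule?** No.

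| | 4.4.1, items 2b and 2c | 4.4.2, item 1a |
|---|---|---|
| Study drug | Stop; no condition or prior review attached | Decided by review of the individual case |
| Left to a provider | In 2b, only whether to use a different anticoagulant | Whether study drug ends; investigators may help |
| Unblinding | Required in 2b, optional in 2c | Not mentioned |

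**Step 4. How does the protocol word a pause, and how an instruction?**
- Where 4.4.1 means a pause, it says so: item 2a qualifies the stop as temporary and provides for a restart. Items 2b and 2c have no such qualifier and mention no restart of study drug.
- The discretion in 2b concerns an alternative anticoagulant, which presupposes that study drug has ended.
- Within 4.4.2, item 1b uses directive wording for thromboembolic events, and item 1a, directly above it, does not. So 4.4.2 repeats the 4.4.1 rule for thrombosis but not for major bleeding.

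**Step 5. Is continued drug after unblinding dealt with elsewhere?** No. Section 5.8 says only that the study is double blind, and section 7.3 has no provision for a participant who continues study drug with the allocation known.

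**Step 6. Which analyses depend on the rule?**
- *Combined safety endpoint (7.2.1.3) and net clinical benefit (section 7.2):* both compare proportions of patients by a binomial approximation. A patient with a major bleed already counts in each, so what happens to study drug afterwards cannot change that patient's status.
- *Separate tabulation of clinically relevant non-major bleeding (7.2.1.3):* it could change, but only if the same patient later had such a bleed.
- *All-randomized set (7.3) and follow-up (4.4.3):* membership does not depend on drug use, and data collection continues after withdrawal for patients who are willing.
- *Primary efficacy endpoint:* a later thrombotic event in such a patient could depend on exposure. Section 7.2.1.2 also refers once to the period of medication use and once to the 3-month study period. Only a reading tied to actual drug use would make the counting window depend on the stopping rule.
- *Per-protocol set (7.3):* a three-day gap in study drug excludes the participant, so the rule matters here, but this analysis is exploratory.

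**The case against.** The best defence is that the two sections do different jobs. Section 4.4.1 says what to do when the bleed happens; 4.4.2 says when a subject may leave the study. Item 1a could then be the later review that decides whether an immediate stop becomes permanent. A site would stop the drug, the provider would review the case, and both sections would be satisfied. The instruction in 4.4.1 is also phrased as a recommendation, which leaves some room for judgement.

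Part of this stands. A reader might infer that sites could take opposite actions and all be fully compliant. That goes too far: a site that never stops the drug departs from 4.4.1 on any reading. But neither section states the stop-then-review sequence, and the protocol's own vocabulary (step 4 of the working) points against it. The softer verb does not help either, since the protocol uses the same phrasing for thromboembolic events, where both sections agree that study drug is to stop.

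A reader might also infer that divergent handling would shift later bleeding counts between sites. The documents do not support this. The tested bleeding endpoint counts each patient once, the affected patients already count, and section 7.2 plans no analysis of bleeding by site.

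Finally, a reader might try to put a number on it by applying a published major-bleed rate to 125 patients per arm. The rates in the documents do not allow this. The 0.6% in section 1.4 is for apixaban over 6 months, the 0.8% in section 1.1 is for nadroparin given for 42 days, and the registry's 1.0% at 3 months comes from calf-vein patients of whom most, but not all, were anticoagulated. None is a 3-month apixaban rate in this population. Placebo patients, who fall under the same rule, would need a rate as well.

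**Conclusion.** The point holds as an internal contradiction between two operative safety passages: wrong as written, not a design choice. It rests on the wording alone, on reading item 1a as a rule about study drug (which it says it is), and on there being no text that orders or ranks the two sections.

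The case for acting is patient safety and consistent handling across sites, including the open question of whether an unblinded patient could continue study drug. The statistical consequence is slight. The combined safety endpoint and the all-randomized analysis set are essentially unaffected, and no effect on alpha, power or sample size is shown. What remains is possible exposure-related change in a few patients' later efficacy or non-major bleeding outcomes, and in the exploratory per-protocol set. The number of such patients cannot be stated, because the documents assume no major-bleed rate for this trial. No view is taken on which clinical rule is right.

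**What to change.** Reconcile 4.4.1 items 2b and 2c with 4.4.2 item 1a into one rule for study drug after a major or life-threatening bleed. The sponsor and its clinicians should choose the rule. State it in full in one section and have the other refer to it instead of restating it.

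The reconciled text should make clear:
- who decides, if any decision is left open;
- whether a stop is temporary or permanent;
- whether study drug can be taken after the patient has been unblinded and, if so, how that participant is recorded and handled in the per-protocol and on-treatment analyses.

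The cost is a protocol wording change, submitted to the IRB as section 11 requires for amendments, and a note to the three sites. Sample size, alpha and the planned tests do not change.

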#### **4.4.3 Data Collection and Follow-up for Withdrawn Subjects**

For subjects withdrawn from the study, follow-up data will be collected throughout the protocol defined follow-up period. This is regardless of compliance or tolerance with study medication, provided participants are willing to provide follow up examinations. This data is important to the integrity of the final study analysis since early withdrawal could be related to the safety profile of apixaban. If a subject withdraws consent to participate in the study, for subject safety reasons, attempts will be made to obtain permission to collect follow up information, whenever possible.

### **5 Study Drug**

#### **5.1 Description**

Apixaban, an oral factor Xa inhibitor, will be provided as a 5 mg tablet or matching placebo.

#### **5.2 Treatment Regimen**

Patients randomized to apixaban will be treated with 10 mg twice daily for 7 days followed by 5 mg twice daily for 3 months. Patients assigned to matching placebo will take their tablets in a similar fashion.

#### **5.3 Ultrasound surveillance**

Following the initial diagnostic duplex ultrasound establishing the presence of a calf vein thrombosis, all subjects, regardless of randomization, will undergo serial follow

up venous ultrasound imaging of the original involved lower extremity at 7 days, 14 days and 3 months. All images will be compared to the original study by a radiologist dedicated to the ultrasound practice but blinded to treatment allocation. The standard ultrasound imaging protocol used for clinical DVT assessment will be used for this study without modification. The patient will be positioned supine with slight reversed Trendelenburg (10°) on the examination table with the hip externally rotated and the knee slightly flexed in an outward position (“Frog leg” posture). A linear ultrasound probe adjusted to the LEV setting at 9MHz will be optimized to depth, gain and focal zone. Venous imaging will begin at the common femoral vein and continued throughout the leg and foreleg to the calf veins carefully assessing each deep venous segment. The great saphenous vein is also imaged in this manner however an extension of thrombus into this superficial vein will not be included as an efficacy endpoint. Image acquisition will include grey scale cross-sectional imaging of each venous segment with and without compression. Color imaging will be included for each venous segment to confirm patency. Once the calf DVT is identified, both the distal and proximal most extent of the thrombus will be marked on the skin using a skin pen. The thrombus length will then be measured and recorded by measuring the distance from the distal to the proximal skin mark. For those patients with multiple calf vein involvement, the length of each thrombus should be measured and recorded. Images will be compared side by side with the archived original study to determine whether thrombus propagation has occurred. All images will be interpreted by a radiologist with expertise and dedication to vascular ultrasound but blinded to treatment allocation. All images will be archived in our PACs system.

